5. To assess pre-trial expectations and post-trial experiences regarding the therapeutic effects of the Zoles insoles and understand their influence on the efficacy of the intervention within the specific subgroup of participants with high baseline pain levels.

Methods

Trial design

The ZOLES trial is a pragmatic, outcome assessor blinded, randomised, controlled, superiority trial, with a two-group parallel design, and a 1:1 allocation ratio. Frequent recreational runners will undergo foot scanning and thereafter be randomised to either receive a customised 3D-printed insole (Zoles ApS, Esbjerg, DK-3060, Denmark), or to be in a “do-as-usual” control group. The pragmatic design and pre-planned secondary analyses are heavily inspired by the SExSI trial [39].

The trial protocol is based on the "PREPARE Trial guide" [35] and adheres to the "SPIRIT 2013 explanation and elaboration: guidance for protocols of clinical trials" [40] and SPIRIT checklist (Appendix A). The trial report will follow the “REPORT guide” [41], and thus adhere to the CONSORT guidelines for reporting parallel group randomised trials [42], using the CONSORT extension for pragmatic trials [43], as well as the updated CONSORT-Outcomes 2022 extension [44]. The TIDieR template (Appendix B) is used to describe the intervention to aid future replication [45].

The study was approved by the St Mary’s University Ethics Sub-Committee on 4 August 2023, and the trial was pre-registered at ClinicalTrials.gov on 4 September 2023 (ID: NCT06034210) [46], before the first participant was enrolled on September 16, 2023.

Study setting

Participant screening and enrolment for this study is undertaken from Faculty of Sport, Technology and Health Sciences at St Mary’s University (Twickenham, London, United Kingdom), with recruitment to the trial being carried out at local parkrun communities, primarily from Bushy Park (Richmond upon Thames, London, United Kingdom).

Eligibility criteria

Inclusion criteria

- a) Participant is ≥ 35 years old at commencement of trial.
- b) Participant can read, speak, and understand English.
- c) Participant can receive e-mails and complete online questionnaires.
- d) Participant is a frequent runner who participate in regular parkrun activities.
- e) Participant is capable of running at commencement of trial.

Exclusion criteria

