The sample size estimation is based on the primary outcome, running-related pain. Lopes et al. [9] reported a median pain level of 3 (IQR: 2-5) among 1049 recreational runners. We expect similar pain levels at baseline which, if normally distributed, should result in a mean pain of 3 and a standard deviation of 2.22 ($SD \approx IQR/1.35$). We forecast a 40% reduction in running-related pain in the intervention group over the course of the trial (from baseline to follow-up). Using the formula $n = (Z_{\alpha/2} + Z_{\beta})^2 * 2\sigma^2/d^2$, where d is the expected difference between groups, to detect a 40% reduction in pain (1.2 units) with 80% power at a 5% significance level, we initially require 70 participants per group [50]. Factoring in an anticipated 15% dropout, this number increases to 82 participants per group. To accommodate the pre-planned secondary subgroup analyses in the future, we further inflate the number by approximately 20%, leading to a total of 100 participants in each group. Hence, this study aims to recruit a cumulative sample size of 200 participants.

Recruitment

Participants are primarily targeted and approached within the local London parkrun communities. Following their routine Saturday 5-km run, a strategic engagement occurs where they will be approached by study representatives. The parkrun offers a natural setting to converse with potential participants who are already involved in regular running activities. During this engagement, participants are presented with an oral briefing about the study, its objectives, and the potential benefits of their participation. This method not only taps into a pool of runners but also allows for immediate interaction, answering any initial queries they might have. Interested runners, eager to contribute or benefit from the study, are subsequently invited to the Biomechanics Laboratory of the Faculty of Sport, Technology, and Health Sciences at St Mary's University in Twickenham, London, UK. Here, they are introduced to

the broader scope of the study, the commitment expected from them, and the potential implications of the research, and ultimately a formal enrolment into the study.

Allocation

Upon completion of the baseline questionnaires, participants will be equally distributed (1:1 ratio) to the two comparison groups (intervention group and “do-as-usual” control group) using a balanced block randomisation method.

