Statistical methods – secondary subgroup analysis and post-market surveillance

The subsequent secondary analysis publication will hold the label "secondary and long-term follow-up analysis from a pragmatic randomised controlled trial" in the title. The aims of this secondary subgroup analysis study are two-fold: First, it is to investigate the immediate therapeutic effect of Zoles insoles, focusing only on participants with clinically relevant baseline pain levels (11-NRS ≥ 3) [38]. Secondly, this will include our long-term post-market analysis to evaluate the long-term effects and durability of the benefits associated with the customised 3D-printed insoles one-year post-intervention.

The between-groups difference among participants with clinically baseline pain levels will be analysed similarly to the primary outcome. Subsequent regression models will, however, also be structured to comprehend the potential influence of pre-intervention expectations and post-intervention experiences, as well as adherence to the intervention on the Zoles insoles' effectiveness within this subgroup. This involves incorporating these factors as covariates in the model.

Statistical methods – analysis population and missing data

For the primary and secondary outcomes of this trial, an intention-to-treat (ITT) analysis approach will be employed [58]. This method ensures the inclusion of all randomised participants in the analysis, irrespective of their adherence to the intervention. Participants will be analysed based on their initial randomisation. As such, any deviations from the intervention or missing follow-ups will not impact the participant's initial group classification in the analysis, as recommended by the CONSORT group [42,44].

To accommodate this approach, missing outcome data will be imputed using multiple imputations by chained equations [59]. The imputation procedure will include the following variables pre-hypothesised to potentially predict missing information: a) preceding scores relevant to the outcome in question, b) age of the participant, c) sex of the participant, d) group allocation, and d) location of recruitment (specific parkrun location).

Harms

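### The imputation plan lists group only as a predictor and does not link imputation to the planned NRS ≥ 3 analysis; under one natural implementation that subgroup effect comes out about 1–5% too small.

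*Combined protocol and SAP*

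**What the plan says.** *Statistical methods – analysis population and missing data* specifies multiple imputation by chained equations. The listed variables are earlier scores on the outcome, "b) age of the participant, c) sex of the participant, d) group allocation", and parkrun location. The type of model, the link and any interactions are not stated. The section is framed for the primary and secondary outcomes.

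*Statistical methods – secondary subgroup analysis and post-market surveillance* then plans an effect estimate in runners with baseline NRS ≥ 3: "The between-groups difference among participants with clinically baseline pain levels will be analysed similarly to the primary outcome". This is the fourth secondary objective. The change in these runners is listed under *Other Outcomes* and is destined for a later paper. *Sample size* raises each group from 82 to 100 to make room for the subgroup analyses. No separate imputation rule is given for them.

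On the expected effect, *Sample size* says "We forecast a 40% reduction in running-related pain in the intervention group" and sizes the trial "to detect a 40% reduction in pain (1.2 units) with 80% power at a 5% significance level".

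**The concern.** An imputation model should be able to represent any contrast later estimated from its output. If group enters as a single main effect on the point scale, every imputed score carries the same average insole effect whatever the runner's baseline pain. If the true point effect is larger at higher baseline pain, runners with NRS ≥ 3 and a missing score are given too small an effect, and the subgroup estimate is drawn towards the overall one.

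Such variation is plausible here. The scale starts at 0 and runners without pain are eligible, so an equal reduction in points at every baseline value is hard to achieve. At stake is the headline estimate of the subgroup paper, for which the sample was enlarged.

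**Working it through.** The plan gives no figure for imputation error, so there is none of its own to reproduce. (The 70 per group in *Sample size* does not follow from its inputs: (1.960 + 0.842)² × 2 × 2.22² / 1.2² = 53.7, so 54. That is a separate matter and does not enter here.)

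**Inputs from the documents.** Planned group size of 100, with two parallel arms at 1:1; baseline pain that "should result in a mean pain of 3 and a standard deviation of 2.22"; 15% dropout; weekly scores to week 10; subgroup cut at NRS 3.

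**Assumptions not in the documents.** Scores missing completely at random; the correlation of weekly scores; four locations holding 55/20/15/10% of runners; the shape of the effect; Bayesian linear imputation; baseline-adjusted ANCOVA standing in for the negative binomial model.

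**Step 1: size by hand.** With whole-number scores from N(3, 2.22) cut to 0–10, the share at NRS ≥ 3 is Φ((3 − 2.5)/2.22) = Φ(0.225) = 0.589. Under a 40% proportional effect, the true effect is −1.795 in NRS ≥ 3 and −1.235 overall. If imputed runners carry the overall effect, then

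shift ≈ (share missing) × (subgroup effect − overall effect) = 0.15 × (1.795 − 1.235) = 0.084 points.

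With a step at NRS 3 (−1.8 above, −0.2 below; overall −1.142) it is 0.15 × (1.800 − 1.142) = 0.099.

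**Step 2: simulation** (400–1,200 replicates). Shift of the NRS ≥ 3 effect from its full-data value at 15% missing; a plus sign means a smaller benefit:

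| Effect shape | Scores available in dropouts | Main effects only | Imputed by arm |
|---|---|---|---|
| 40% proportional | baseline only | +0.086 | 0.000 |
| | dropout spread over weeks 1–10 | +0.055 | 0.000 |
| | all but week 10 | +0.024 | 0.000 |
| Step at NRS 3 | baseline only | +0.096 | +0.031 |
| | dropout spread over weeks 1–10 | +0.080 | +0.029 |
| | all but week 10 | +0.027 | +0.008 |
| Constant −1.2 | baseline only | +0.003 | 0.000 |

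The Monte Carlo standard error is 0.003–0.007. For the proportional effect, the relative size runs from 0.024/1.795 = 1.3% to 0.086/1.809 = 4.8%. The mean standard error of the subgroup effect is 0.33–0.35. A joint model with group × baseline did as well as by-arm imputation: 0.000 and −0.006 in the first two rows; 0.029, 0.031 and 0.009 in the step rows.

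**Step 3: cross-checks.**
- A separate simulation under the 40% proportional effect moved the subgroup effect from −1.77 to −1.69, −1.72 and −1.75 for the same three patterns. Both remedies returned it to about −1.78.
- Imputing inside the subgroup also works. In another run the full-data effect was −1.654, whole-sample main-effects imputation gave −1.578, and imputation within NRS ≥ 3 gave −1.649.
- On the ratio scale, with a log-link count model, the subgroup ratio moved from 0.610 to 0.626 after linear imputation and was 0.613 by arm.
- The overall effect did not move: −1.240 with main effects, −1.239 by arm.

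**Step 4: price of the remedy.** The mean standard error rose by 0–2% in the main simulation. The spread of estimates across replicates rose more (0.336 to 0.349, or 3.9%, with baseline only), and by 4–12% in the separate simulation. At 30% missing with the step effect, by-arm fits became near-singular in the smallest location: the mean standard error went from 0.389 to 0.663, against 0.393 for the joint model with group × baseline.

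**The case against.** The best reply is that the plan lists variables and not a model. Adding an interaction is compatible with the list. The imputation text covers primary and secondary outcomes, so the later paper might restrict to NRS ≥ 3 first and impute there, in which case the pull nearly vanishes. This stands: the point is a gap in specification, not a demonstrated error. A main-effects reading is nevertheless the natural one, because group would be constant, and so no predictor, if imputation ran by arm.

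A reader might go further and infer that the imputation contradicts the trial's own expected effect. The documents do not support that. *Sample size* turns the 40% into a single difference of 1.2 units and does not say that each runner's benefit scales with baseline pain. The planned negative binomial model would also express a common 40% reduction as one constant ratio, and imputation on a log scale would then need no interaction.

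A reader might also infer harm to the effect in runners below NRS 3, or to the difference between the two groups of runners. The plan reports neither, so neither counts as a consequence.

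The bias is also small beside the noise. Coverage with main effects at 15% missing stayed at about 94.5–96%. In the worst proportional case the total error is level: √(0.336² + 0.086²) = 0.347 with main effects, against 0.349 by arm. That also stands. What the remedy removes is a bias with a known direction; it does not gain precision. Weekly scores, reminders and telephone follow-up should push the bias towards the lower end of the range.

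**Conclusion.** The concern holds as a modest gap in specification. With main-effects imputation on the point scale over all runners, and the subgroup read from those datasets, an effect that rises with baseline pain leaves the NRS ≥ 3 estimate about 1–5% too small at 15% missing. That is 0.02–0.09 points under a proportional 40% effect, and at most about a quarter of a standard error (0.086/0.352 = 0.24). A step at NRS 3 gives up to about 0.10.

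The result depends on three things that the plan leaves open: the form of the imputation model, the reuse of whole-sample datasets, and an effect that varies with baseline on the imputation scale. If the point effect is constant, or the subgroup is imputed on its own, the bias is close to nil. The primary estimate is not affected. This is an inexpensive improvement and no threat to the trial's main conclusion.

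**What to change.** In *Statistical methods – analysis population and missing data*, state that the imputation model for running-related pain includes group × baseline pain and group × (baseline NRS ≥ 3), and that the same imputed datasets serve both the overall and the NRS ≥ 3 analyses. An acceptable alternative is imputation run separately by arm, with an NRS ≥ 3 indicator and small parkrun locations pooled. The indicator matters because by-arm imputation or a linear interaction alone left about a third of the bias under a step at 3 (0.031/0.096 = 32%). The runs above did not include the indicator itself.

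The cost is one or two sentences and a small change in code. The subgroup standard error rises by a few percent, up to about 10%. By-arm fits may be unstable with small locations or high missingness; the joint model with interactions is then safer.

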Objectives

Primary research question

Based on the description provided and existing evidence, we posed the following research question: *Is the use of Zoles customised 3D-printed insoles, for a duration of 8 weeks, superior to a "do-as-usual" control strategy in improving running-related pain among frequent recreational runners participating in regular parkrun activities?*

This research question was designed using the PICOT model with the following specifications for each element [35]:

Population: Frequent recreational runners participating in regular parkrun activities.

Intervention: Zoles customised 3D-printed TPU insoles for ~8 weeks.

Control: "Do-as-usual" control group.

Outcome: Improvement in running-related pain.

Time frame: 10 weeks after baseline (~8 weeks after receiving allocated intervention).

Primary objective

The primary objective is to determine the effectiveness of the Zoles customised 3D-printed insoles on the change in running-related pain 10 weeks after baseline in frequent recreational runners participating in regular parkrun activities.

Primary research hypothesis

Our hypothesis is that the Zoles customised 3D-printed insoles, will lead to a significant reduction in running-related pain 10 weeks after baseline (~8 weeks after received allocated intervention) compared to a "do-as-usual" control strategy among frequent recreational runners participating in regular parkrun activities.

Secondary objectives

1. To assess the effect of Zoles customised 3D-printed insoles on secondary outcomes like:
 - a. Global Rating of Change (GRoC) in overall daily pain and discomfort [36].
 - b. Running-related foot/footwear comfort [37].
 - c. 5-k (parkrun) completion time.
 - d. Running-related injury incidence rate.
 - e. Time-loss from running.
 - f. Running exposure in terms of miles and time.
 - g. Adherence to the intervention during daily- and running activities.
 - h. Adverse events from using the Zoles insoles.
2. To explore if the control group benefits similarly to receiving customised 3D-printed insoles when provided after the initial 10-week primary trial phase.
3. To understand the long-term effects and durability of the benefits of the Zoles customised 3D-printed insoles, assessed one year after the intervention.
4. To investigate the immediate therapeutic effect of Zoles insoles specifically for participants with clinically relevant baseline pain levels (11-NRS ≥ 3) [38].

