- **Running-related injuries:** The incidence rate of injuries related to running will be monitored and reported as the number of injuries for every 1000 hours of running exposure over the 10-week duration.
- **Time-loss:** The total number of days participants miss out from running due to pain, discomfort, or injury will be tracked weekly for 10 weeks, and again at the 18-week mark.
- **Weekly Mileage:** The distance participants run every week will be recorded during the 10-week trial period, and again at the 18-week mark.
- **Weekly running exposure:** The total time participants spend running every week will be obtained in hours and minutes for the 10-week trial period, and again at the 18-week mark.
- **Adherence to intervention, ADL%:** This outcome tracks how frequently participants use the Zoles insoles for everyday activities such as sitting, standing, walking, and driving over the 10 weeks, and tracked again at the 18-week mark, and at the 52-week post-market surveillance.
- **Adherence to intervention, RUN%:** The percentage of time participants wear the Zoles insoles specifically during running will be monitored over the 10 weeks, and again at the 18-week mark, and at the 52-week post-market surveillance.
- **Adverse events from using Zoles insoles:** All adverse events associated with the usage of Zoles will be reported based on their type and number. Throughout the trial, participants will be encouraged weekly to report any adverse events through the trial

hotline. Participants will be asked again at the 52-week-post-market-surveillance to capture any long-term events.

Other Outcomes

The other outcomes of interest for the pre-planned secondary subgroup analyses include:

- **Participants achieving MCID reduction in pain:** This measure looks at the percentage of participants who manage to achieve a clinically meaningful reduction in running-related pain, defined as a reduction equal to or larger than the MCID (NRS \geq 2) as described by Salaffi et al. [48] over the 10 weeks.
- **Time until MCID reduction in pain:** This outcome gauges the time in weeks it takes for participants with clinically significant pre-existing pain (NRS \geq 3 as defined by Rathleff et al. [38]) to achieve the clinically meaningful reduction in running-related pain (MCID) during the 10-week trial period.

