The allocation phase (Timepoint 0) commences post-enrolment, where participants are sent a baseline questionnaire. The information gathered from this questionnaire is used in the balanced block randomisation procedure. Upon completion of the baseline questionnaire, participants are set up to receive weekly follow-up surveys during the primary study period (Weeks 1-10). During this period, there is weekly follow-up on primary and secondary outcomes, delivery of allocated intervention group insoles projected before week 3, and weekly monitoring of adherence and adverse effects. In a case where a pair of insoles do not fit inside a participant's footwear, a fast-track adjustment, production, and shipment procedure takes place, ensuring a minimal delay of insole delivery of approximately one week.

In the control group step allocation period (Weeks 10-18), control group participants receive their customised insoles and all participants are sent a single event follow-up questionnaire at week 18. This questionnaire covers primary and secondary outcomes, as well as adherence and adverse effects.

Finally, post-market surveillance occurs at Timepoint Week 52, a year after the study's commencement. All participants receive a follow-up questionnaire assessing their post-trial experiences with the insoles, any adverse effects experienced during the year, and the long-term effects of the Zoles insoles (Figure 3).

Sample size

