In adherence to transparency and scientific scrutiny, a fully anonymised dataset at the participant level, accompanied by the corresponding statistical code, will be made available to the public, contingent upon the requirements of the journal publishing the study's findings. This disclosure ensures the replicability and verification of the research while upholding the anonymity and privacy of all participants.

The published results will omit any information that could potentially be used to identify individual participants.

Statistical methods

The primary outcome; change in running-related pain from baseline to follow-up, will be calculated using negative binomial regression. Figure 4 illustrates a hypothetical change in pain over the course of the trial, including the expected catch-up by the control group at week 18. It is important to note, however, that the between-groups analysis for difference will adjust for

values reported at baseline [49,57]. Both the Global Rating of Change (GROC) in overall daily pain and discomfort and running-related foot/footwear comfort will be calculated similarly. Injury incidence rate ratios will be estimated per 1000 hours of running exposure using Poisson regression. Mean time-loss from running will be calculated using negative binomial regression. Adherence to the intervention will be descriptively analysed and presented, and adverse event due to the Zoles insoles will be presented in type and frequency. Every analysis in the main trial report will abide by the intention to treat principle, which means including all participants in the analyses, regardless of intervention adherence-signifying that participants will be analysed based on initial randomisation. In the primary trial report, all collected outcomes will be listed, and it will also be stated that the below-mentioned 'other pre-specified outcomes' will be reported in a subsequent secondary analysis publication with a clear reference to the primary trial registration.

Possible effect modifiers include time with allocated intervention due to possible logistics issues in handing over the insoles to the intervention group, as well as any last-minute needs for sizing adjustments if a pair of insoles do not fit inside a participant's footwear. Any new injury sustained during the trial period is another potential effect modifier. No potential external effect modifiers will be factored in the intention-to-treat analyses.

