Adverse events, within the context of this study, are defined as any unintended symptoms, injuries, or illnesses that participants experience while being allocated to the intervention, regardless of attribution. These could manifest anytime following the introduction of the 3D-printed insoles and until the one-year follow-up.

The recording of these events is pivotal and will be initiated by the participants through spontaneous reporting. Every interaction with participants, be it during prospective follow-ups or the post-market surveillance stage, will underscore the importance of reporting any and all adverse effects. Participants will be systematically reminded of this imperative, ensuring a thorough and comprehensive documentation of potential adverse events associated with the use of the insoles. Regular auditing planned throughout the study in the form of pre-scheduled meetings between the principal investigator (SI), study director (FGL) and local study chair (RM).

Serious adverse events are categorised according to the criteria established by the United States Food and Drug Administration [60]. The primary investigator undertakes the responsibility of evaluating these events, assessing their potential association with the intervention. Every incident is examined to discern if there is a reasonable possibility that the insoles contributed to the adverse event. In the unfortunate occurrence of serious unexpected adverse events, these will be immediately reported to the St Mary's University Ethics Sub-Committee within 7 days of the event's occurrence.

Ethics and dissemination

This study is anchored in stringent ethical guidelines, ensuring alignment with the World Medical Association (WMA) Declaration of Helsinki and adherence to the General Data Protection Regulations (GDPR) under the Data Protection Act 2018. Ethical approval was granted from St Mary's University Ethics Sub-Committee on August 4, 2023. Consistent with the recommendations of the CONSORT group [42] and the International Committee of Medical Journal Editors (ICMJE) [61], the study was pre-registered on ClinicalTrials.gov on September 4, 2023. To maintain transparency and ethical integrity, any modifications to the protocol will be duly updated on ClinicalTrials.gov, communicated to the University Ethics

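### Adverse events are defined regardless of attribution but reported by attribution to the insoles, and control participants fall outside the definition in weeks 0–10

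*Combined protocol and SAP*

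**What the plan says.** **Definition (Harms).** Adverse events are "any unintended symptoms, injuries, or illnesses that participants experience while being allocated to the intervention, regardless of attribution". On timing, the section adds: "These could manifest anytime following the introduction of the 3D-printed insoles and until the one-year follow-up".

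**Reporting.** Three other places describe what is reported, each by link to the product:
- Secondary objectives, item 1h: "Adverse events from using the Zoles insoles".
- Secondary outcomes: "All adverse events associated with the usage of Zoles will be reported based on their type and number".
- Statistical methods: "adverse event due to the Zoles insoles will be presented in type and frequency". No between-group analysis of adverse events is described.

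**Recording in weeks 1–10.** Harms says that recording "will be initiated by the participants through spontaneous reporting". Secondary outcomes says that "participants will be encouraged weekly to report any adverse events through the trial" hotline. Participant timeline lists "weekly monitoring of adherence and adverse effects" for the same period.

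**Later recording.** The week-18 questionnaire, sent to everyone, covers adverse effects, and participants are asked again at week 52. Controls receive insoles after week 10.

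**The concern.** An event that meets the Harms definition but is judged unrelated to the insoles has no stated place in the primary report. Two analysts could build different harms tables from the same records, and each could cite the protocol.

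Attribution is a weak filter in this trial. Participants know their group, and the Discussion accepts that a wish to please may affect self-report. Harms gives the judgement of relatedness to the primary investigator, in a paragraph that opens with serious events, and does not say that this person is blinded.

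The Discussion also describes pain and niggles as common in active runners. Without a concurrent count in controls, background symptoms cannot be separated from insole effects. That could hide a harm, or it could blame the product for events that would have happened anyway. The missing count cannot be recovered later, because controls have insoles after week 10.

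**Working it through.** The plan states no adverse-event rate, capture rate or safety sample size, so there is no figure to reproduce. The check sets the sections side by side, then gives some arithmetic for scale.

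**1. Definition against reporting.** Harms rules out attribution as a condition. The objective, the outcome and the statistical text each use it, in three different wordings (from using, associated with, due to). An unrelated illness in an insole user is an adverse event under the first and is not reportable under the other three.

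**2. Who can have an adverse event, and when.**

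| Period | Insole arm | Control arm |
|---|---|---|
| Randomisation to insole delivery (projected before week 3) | Allocated, but before the stated window opens | Outside the definition |
| Delivery to week 10 | Inside | Outside the definition |
| After week 10 | Inside | Has insoles; no longer a comparator |

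No row has both arms counted while only one has insoles. Adverse events are nevertheless listed as a secondary outcome, and the section on analysis population promises that all randomised participants are included for primary and secondary outcomes.

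**3. What is compared in the randomised weeks.** Statistical methods plans a Poisson rate ratio for running-related injuries and negative binomial models for running-related pain, global rating of change, comfort and time-loss. Skin problems, falls, non-running injuries, illness and other individually identified symptoms are not covered. These matter because participants are encouraged to wear the insoles in all daily activities as well as for running.

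**4. Scale. All risks and capture fractions below are assumptions; 100 per arm and 15% dropout are from Sample size.**

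- *Capture.* Recorded = 100 × risk × capture. At a true risk of 10% and 25% capture: 100 × 0.10 × 0.25 = 2.5 affected participants recorded out of 10. At 30% and 75%: 100 × 0.30 × 0.75 = 22.5 out of 30. The range only shows how far an unknown capture fraction matters.
- *Zero events.* The one-sided 95% upper limit is 1 − 0.05^(1/n). For n = 100 it is 3.0%; for n = 100 × 0.85 = 85 it is 3.5%. This assumes complete capture.
- *Precision by arm.* For 30% v 20% with 100 per arm: SE = √(0.30 × 0.70/100 + 0.20 × 0.80/100) = √0.0037 = 0.061. The difference is 0.10 ± 1.96 × 0.061, or about −0.02 to +0.22.
- *Power, two-sided 5%, n = 100 per arm.* Power = Φ{[|p₁ − p₂| − 1.96√(2p̄(1 − p̄)/n)] / √[p₁(1 − p₁)/n + p₂(1 − p₂)/n]}, where p̄ is the mean of p₁ and p₂. This gives 0.66 for 5% v 15%, 0.80 for 10% v 25%, 0.37 for 20% v 30% and 0.88 for 20% v 40%. Only large differences would be detected.

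**The case against.** The strongest reply has four parts.

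- **Harm is already compared.** The adverse-event definition includes injuries, and running-related injuries have a planned between-group rate ratio. The global rating of change runs down to much worse, and pain, comfort and days lost are collected weekly. This stands. A reader might infer that the trial has no randomised comparison of harm at all, and the documents do not support that. The gap is the set of events outside those outcomes.
- **Reporting is not by hotline alone.** Harms says that participants are systematically reminded, and questionnaires ask about adverse effects at weeks 18 and 52. This also stands, but both questionnaires fall after the randomised contrast has ended.
- **The weekly survey may already ask.** Appendix G is listed but its content is not available here, and the adverse-event row of Figure 3 cannot be read in this text. It would be wrong to conclude that an item is missing. The recording descriptions still differ and need one answer.
- **The attribution wording may be a sequence.** The plan could mean: record everything, judge relatedness, then present the related events. Statistical methods does not say that only related events will be shown. That reading is possible, but it leaves unrelated events without a table and does nothing for the control arm.

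**Conclusion.** The point holds as a conflict of definition and reporting, together with a limited gap in the randomised comparison. The plan defines adverse events regardless of attribution, reports them by attribution, and gives controls no window in weeks 0–10. Beyond the injury, pain, global rating, comfort and time-loss outcomes, harms have no concurrent comparator.

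A reader might go on to conclude that harms are under-counted. Spontaneous reporting makes that plausible, but no capture rate is given, so neither the fact nor the size can be established from the documents.

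The conclusion rests on the stated wording alone. It would soften if the weekly questionnaire already asks both arms the same question; then only the definition, the window and the table would need to change. Since 100 per arm gives intervals roughly 24 points wide in the example above, the value of a by-arm table lies in estimation and in removing the attribution filter, not in testing.

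**What to change.** 1. Extend the adverse-event definition to all randomised participants, with the window opening at randomisation in both arms.
2. In the primary report, tabulate all events regardless of attribution by randomised arm for weeks 0–10, with the risk difference and 95% CI, labelled descriptive. Show events judged related to the insoles in a second table, and state who judged them and whether that person knew the allocation.
3. If the weekly questionnaire does not already ask about adverse events in both arms, add one structured item, identical in both (for example, whether there was any new symptom, injury or illness this week). Record the date it was introduced.
4. Reconcile Secondary objectives, Secondary outcomes, Participant timeline, Statistical methods and Harms on definition, recording route and reporting.

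**Cost.** One table, at most one short survey item, and the notice to registry and ethics committee that the plan requires for modifications. More non-specific events will be listed. Recruitment ran from 16 September to 2 October 2023 and the protocol version is dated 27 September, so surveys may already have begun. Capture could then be uneven in the first weeks, and the table should say which weeks were asked about in the same way in both arms.
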